**C.14.3.** Aim 3 (Exploratory): To explore the effect of caregiver outcomes (self-care, stress, coping, health status) on HF patient outcomes. We hypothesize that at 12 months, HF patients whose caregivers improve vs. not improve in self-care (regardless of group) will have H3a: Lower hospitalization rates; H3b: Fewer hospital days; H3c: Lower mortality rates; and H3d: Higher QALYs measured with the SF-6D. We will analyze number of hospitalizations and days in the hospital using GEE regression models with the Poisson distribution as the working outcome distribution. GEE allows for modeling of the marginal distribution of each outcome variable as a function of the caregiver predictor of interest over time, and accounts for the likely correlations of the repeated outcome measures for each participant. An approach similar to that described for Aim 1 will be used within the GEE framework (different correlation structures will be examined, baseline outcomes will be included as a covariate).

We will measure time to death from date of the caregiver's enrollment in the study to the date of patient death. Patients remaining free from an event will be censored at their last follow-up. Kaplan-Meier estimates will be plotted to provide a visual demonstration of time to death by group (categorized caregiver outcomes), and the log-rank test will be used for comparisons. GEE and frailty type multivariable modeling will be applied to time-to-event data within the context of equally spaced time intervals. This approach allows for the addition of a random effect to a general Cox proportional hazards model to account for the likely correlation of repeated measures for each study participant while also accounting for censoring.

QALYs will be analyzed using mixed effects regression modeling. As described above, scores will be analyzed as repeated observations, with mean-centered baseline outcome scores serving as a covariate. Other predictor variables will include time-dependent caregiver variables, assessment time, and the corresponding two-way interaction term (primary effect of interest). Statistically significant findings will be concluded on the basis of a two-sided 0.05 level of significance, recognizing these analyses are exploratory in nature and findings will be used to generate hypotheses. Finally, we will examine the effect of caregiver outcome on HF patient outcomes in patient-caregiver dyads using the Actor-Partner Interdependence Model.

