Using a randomized controlled trial (RCT) design, we will enroll informal HF caregivers with poor self-care (Health Self-Care Neglect scale score ≥2), randomizing them 1:1 to an intervention or control group. Both groups will receive standard care augmented with Health Information (HI) delivered through the Internet, but the ViCCY caregiver group will also receive 10 front-loaded coaching support sessions tailored to individual issues. The control group will have access to the same HI resources over the same interval, using the same Internet program, but without coaching support. At baseline and 3, 6, 9, and 12 months, we will collect self-reported data on self-care, stress, coping, and health status. At 6 months, we will compare the efficacy of ViCCY (HI plus coaching) to HI alone to assess intervention efficacy using intent-to-treat analysis. Our pilot data suggest that addition of support provided by the health coach will make ViCCY more efficacious than HI alone. A sample of 250 caregivers (125/arm) will provide >90% power to detect significant differences between the groups on the primary outcome of self-care (Aim 1). We will collect quality adjusted life years (QALYs) and health care resource use in caregivers over 12 months to assess cost-effectiveness of ViCCY (Aim 2). To explore the effect of caregiver outcomes on HF patients' outcomes over a 12-month period (Aim 3) and knowing that not all HF patients will participate, we will consent a subgroup of the HF patients cared for by these caregivers (at least 40 dyads). We have the following Specific Aims:

- Aim 1: To compare the efficacy of ViCCY vs. HI alone in improving self-care. We hypothesize that, at 6 months after enrollment, caregivers randomized to ViCCY vs. HI alone will have **H1a**: Improved self-care measured with the Health Self-Care Neglect scale (*primary outcome*); **H1b**: Less self-reported stress measured with the Perceived Stress Scale (*secondary outcome*); **H1c**: Better coping measured with the Ways of Coping Questionnaire, short form(*secondary outcome*); and **H1d**: Better perceived mental and physical health status measured with the SF-36(*secondary outcome*).

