- **C.4.c Consideration of Sex as a Biological Variable.** In accordance with NIH guidance, we will include sex as a biological variable in study design (block randomization of men and women to each group), analyses, and reporting. We will report all primary and secondary outcomes separately by sex to enhance the rigor and transparency of our findings. We expect to enroll more female than male caregivers because most HF caregivers are female and support interventions are more appealing to women. Enrolling at least 50 men is a goal so that sex-related differences in intervention efficacy and outcomes can be identified. We will monitor enrollment weekly. If fewer than 15 male caregivers are enrolled in the first 3 months, we will conduct a focus group with male caregivers to identify specific elements that could be emphasized to make the intervention more attractive to them.
- **C.4.d. Randomization and Blinding.** Block randomization will be used to achieve equal distribution of key variables in each condition. We will block randomize on caregiver sex (male/female) and relationship to patient (e.g., spouse) factors shown to influence perceived caregiving burden and receptivity to intervention. The randomization sequence will be generated *a priori* by a statistician independent of the study investigators using a randomly permuted blocks algorithm to ensure equal distribution of these variables in each study arm. The Project Manager will notify the study staff and participants of their group assignment (ViCCY or HI only) by telephone, email or message, as preferred by the individual. Although balance in sample size can be achieved with block randomization, the groups may not be fully comparable on other factors. Initial comparison of the groups will allow us to control for important covariates in the analyses. Investigators and all staff involved in collecting assessment data will be blinded to group assignment until after the data are locked. The RN providing the intervention and the caregiver participants will not be blinded. All baseline data will be collected prior to randomizing. Timing of follow-up assessments will be based on day of randomization.

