- C.13. Power. We will enroll 250 caregivers (125 caregivers per study arm) to achieve over 90% power to detect significant overall differences in longitudinal profiles between the groups on the primary outcome of Health Self-Care Neglect Scale. 35 Assuming estimates similar to those in our pilot data, and extrapolating through 6 months, along with control group scores that also decline over time (due to interaction that comes with participation in a clinical trial) but at a slower rate than the intervention, it is assumed that ViCCY caregivers will demonstrate mean Health Self-Care Neglect scores of 3.2, 1.25, 1.1 while HI caregivers will demonstrate mean scores of 3.2, 3.0, 2.7 at baseline, 3, and 6 months, respectively. Combining the two data sets, this translates to mean scores of 1.85 and 2.97 (D=1.12) overall for intervention and control group caregivers, respectively—in line with a clinically meaningful difference equal to 0.4\*SD (SD 2.8)=1.12 units. We conservatively assumed that standard deviations (pilot estimates 2.5 and 1.3 at baseline and 3 months) are constant over time, equal to 2.8, and that the variance-covariance matrix pattern is generated using a mixed effects model design (congruent with the primary analytic plan) with a first-order auto-correlation parameter equal to 0.3. A design with three assessment points and 100 participants per group (200 total) achieves 99% power to test the overall between-group effect (intervention vs. control without regard to changes over time), 99% power to test the overall time effect, and 90% power to test the group x time interaction effect. All tests are based on simulations with 100 iterations, a 5% significance level, mean vectors and variance-covariance as described above. We anticipate 20% attrition based on our prior experience with the intervention, which was found to be helpful, supportive, and stress relieving rather than burdensome. Further, we will remunerate caregivers for their time and effort (see Human Subjects).

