The PI, [name] will oversee the recruitment and enrollment of caregivers. We anticipate enrolling a diverse sample of participants, with many in vulnerable racial, socio-economic, and geographically disadvantaged groups. We acknowledge that there will be too few Asians and Hispanics to analyze in a meaningful way but we will include these caregivers and analyze their data in an exploratory fashion. We expect to enroll women more easily than men because most caregivers are women and this type of intervention is more appealing to women. Recruitment efforts will focus on enrolling a sufficient number of men so that we can analyze sexbased differences in response to the intervention. We will balance sex and the nature of the relationship through block randomization to groups as we enroll. We will not include caregivers of children with HF; HF in a child is unusual. No caregivers who are < 18 years of age will be included because their stresses may be unique. No vulnerable populations will be enrolled.

The randomization sequence will be generated a priori by a statistician unassociated with the study. Study nurses and caregiver participants will be notified of their group assignment by the Project Manager. Both groups will receive Health Information (HI) delivered by the Internet (http://www.nhs.uk/pages/home.aspx) in addition to standard care. The intervention group will receive virtual health coaching (ViCCY) by video conferencing, with 10 front-loaded health coaching contacts over six months. This dose is based on published data demonstrating that six months of health coaching is needed to be effective.

No other collaborating sites are involved.

Sources of materials. The research material obtained from caregivers will be primarily self-report surveys (e.g., self-care, stress, health status) and clinical information such as names of medications. The self-report measures will be collected five times over the course of 12-months (baseline and 3, 6, 9, and 12 months). On enrollment, illness-related information and caregiver burden will be measured.  Quality of the relationship with the patient; social determinants of health; and demographic, caregiving, and clinical characteristics will be gathered from caregivers at enrollment only. Three randomly selected ViCCY sessions delivered by each health coach will be audiotaped, reviewed and rated for fidelity.

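### At the planning SD, the goal of 50 men can reliably detect only a sex difference in efficacy larger than the whole assumed treatment effect, so the purpose stated in C.4.c should be restated as exploratory

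*Combined protocol and SAP*

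**What the plan says.** Section C.4.c (Consideration of Sex as a Biological Variable) sets the target and its purpose together: "Enrolling at least 50 men is a goal so that sex-related differences in intervention efficacy and outcomes can be identified". It also commits to reporting the primary and secondary results for each sex. Under Human Subjects, Protection of Human Subjects, the aim recurs in softer form: "Recruitment efforts will focus on enrolling a sufficient number of men so that we can analyze sexbased differences in response to the intervention".

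C.4.d makes sex a balancing factor in the randomisation. The mixed-model paragraph of C.14 assigns differences by the balancing variables to interaction terms of higher order, so the plan already names the interaction as its test for sex.

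C.13 (Power) gives power for whole-sample effects only. Its benchmark for the group difference averaged over three visits is described as "in line with a clinically meaningful difference equal to 0.4\*SD (SD 2.8)=1.12 units". No section gives a power or a detectable difference for sex. C.14 concedes that the trial is not powered for the secondary outcomes, but says nothing similar about sex.

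**The concern.** A sex difference in efficacy is the treatment effect in men minus the treatment effect in women. Its precision is governed by the smaller group, and 50 men is one fifth of the sample. C.4.c ties a specific number to a specific inference, so it is fair to ask whether that number supports it.

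Two things are at stake. A real sex difference in efficacy would usually be missed. And because results will be shown for each sex, unequal group sizes alone can produce a significant result in women beside a non-significant one in men. C.4.c already says that support interventions appeal more to women, so readers would find that pattern easy to believe.

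**Working it through.** **Inputs**
- 250 enrolled, allocated 1:1 (C.13, Specific Aims). At the floor of 50 men this gives 25 men and 100 women per arm.
- 20% attrition (C.13). If equal by sex (assumed), 20 men and 80 women per arm remain.
- SD 2.8 at every visit, first-order autocorrelation 0.3 (C.13).
- Assumed means at 0, 3 and 6 months: 3.2, 1.25, 1.1 with ViCCY and 3.2, 3.0, 2.7 with HI. The 6-month effect is 2.7 − 1.1 = 1.6.
- 5% level (C.13). C.13 does not give the sidedness; two-sided is stated only for Aim 3 and is assumed here.
- Power for sex: none stated. 80% is assumed, with 90% alongside.

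**Reproducing C.13.** The three-visit means are 5.55/3 = 1.85 and 8.9/3 = 2.967, a difference of 1.117. The SD of a three-visit mean is 2.8 × √[(3 + 4×0.3 + 2×0.09)/9] = 1.953. With 100 per group the SE is 1.953 × √(2/100) = 0.276, and the power is 98.1% against 99% stated. The time effect gives 99.9% against 99%, and 200/0.8 = 250 as stated. For group × time, different forms of the test give 85% to 95%, which bracket the stated 90%; 100 simulations carry a standard error of 3 points. The inputs are therefore read as the plan intends.

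**Interaction at 6 months.** SE = SD × √(2/men per arm + 2/women per arm). Detectable difference at 80% power = (1.960 + 0.842) × SE.
- No attrition: 2.8 × √(2/25 + 2/100) = 0.885, so 2.48 (90% power: 2.87).
- With attrition: 2.8 × √(2/20 + 2/80) = 0.990, so 2.77 (90% power: 3.21).

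Against 1.6 the ratios are 1.55 and 1.73. Power for a sex difference of the full 1.6 is Φ(1.6/0.885 − 1.96) = 44% and Φ(1.6/0.990 − 1.96) = 37%.

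**Other contrasts and SDs (80% power)**

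| Contrast | No attrition | 20% attrition | Whole assumed effect |
|---|---|---|---|
| Three-visit average, SD 2.8 | 1.73 | 1.93 | 1.12 |
| 6 months, baseline-adjusted (correlation 0.09 to 0.3) | 2.47 to 2.37 | 2.76 to 2.65 | 1.6 |
| Mean of 3 and 6 months, baseline-adjusted | 1.94 | 2.17 | 1.675 |
| 6 months, SD 2.5 | 2.21 | 2.48 | 1.6 |
| 6 months, SD 2.0 | 1.77 | 1.98 | 1.6 |
| 6 months, SD 1.3 | 1.15 | 1.29 | 1.6 |

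The detectable difference equals 1.6 when the SD is 1.6/(2.802 × 0.3162) = 1.81 without attrition, or 1.6/(2.802 × 0.3536) = 1.62 with it.

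**More men.** Even an equal split of 250, 125 men and 125 women, gives 1.98 at 6 months. With 20% men, about 600 analysed caregivers would be needed to detect 1.6.

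**Separate results by sex.** Suppose both sexes benefit by 1.6. After attrition, a t-test in women alone (80 per arm) has 95% power and in men alone (20 per arm) 42%. The chance of significance in women but not in men is 0.949 × 0.579 = 55%, with no sex difference present.

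**Precision in men alone.** The 95% half-width is t × 2.8 × √(2/n per arm): about 1.6 points with 50 men analysed (2.01 × 0.792) and about 1.8 with 40 (2.02 × 0.885).

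**The case against.** The best reply is that C.4.c states a recruitment goal in a section on reporting by sex, with no power level attached, and that 80% is the reviewer's choice. That is true. But the sentence still gives the number as sufficient for an inference, and no customary power level rescues it: 90% widens the gap.

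The second reply is that the plan calls 2.8 conservative, and this has force. The scale has ten dichotomous items. If scored 0 to 10, a mean of 1.1 allows an SD of at most √(1.1 × 8.9) = 3.13, so 2.8 is near the ceiling for the ViCCY arm. At the 3-month pilot SD of 1.3 quoted in C.13, the conclusion reverses. That figure comes from four caregivers, however, and the plan did not use it.

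Third, the mixed model uses partial data from those who drop out, so the attrition figures are somewhat pessimistic. The no-attrition figures already exceed 1.6.

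Some stronger readings are tempting but not supported:
- A reader might set 2.77 against 1.12 and call it 2.5 times the meaningful difference. The 1.12 is a three-visit average; like for like the ratio is about 1.5 to 1.7.
- A reader might infer that the plan will judge sex differences by comparing separate p-values. C.14 names the interaction as the test. What is missing is a caution on how the separate results should be read.
- A reader might extend the criticism to the whole sentence. A male-female difference in outcome level, pooled over arms, is detectable at about 1.24 or 1.39 points, so the part about outcomes is not shown wrong.
- The Human Subjects sentence promises only that sex differences can be analysed, which is true.

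**Conclusion.** The concern holds for efficacy, at the 50-man floor and the planning SD. The sex difference in effect that the trial could detect with 80% power is 2.48 to 2.77 points, about 1.5 to 1.7 times the entire assumed 6-month effect. Power for a difference as large as that effect is 44% at best.

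This rests on a two-sided 5% test, an assumed 80% power, attrition equal by sex, and an SD above about 1.8 (no attrition) or 1.6 (with attrition). Fifty is a minimum, but at SD 2.8 no division of 250 by sex brings the 6-month figure down to 1.6.

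The primary analysis, the randomisation and the overall sample size are unaffected. The defect is a design property claimed in C.4.c that the plan's own figures do not support. It matters mainly because results will be published for each sex.

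**What to change.** Keep the goal of 50 men, the stratification by sex and the reporting by sex. Restate the purpose in C.4.c along these lines:
- The analysis of differential efficacy by sex is exploratory. Sex-specific treatment effects are given with 95% confidence intervals; the expected 6-month half-width in men is about 1.6 points with 50 analysed and about 1.8 with 40.
- At SD 2.8 the interaction detectable with 80% power is about 2.5 points without attrition and 2.8 with 20% attrition, against an assumed overall effect of 1.6.
- Any claim of differential efficacy rests only on the interaction already named in C.14 and its confidence interval. A non-significant result in men alone will not be read as lack of effect.

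The Human Subjects text needs no correction. The cost is a few sentences and no added participants. The downside is that the stated claim becomes less favourable. The wording should be settled before results by arm are known.

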experience in cardiac nursing, excellent interpersonal communication skills, and comfort with technology. RNs will receive two days of initial training in health coaching from [name] and then complete a 7-hour online training program in motivational interviewing provided by the University of Colorado, College of Nursing. Thereafter, weekly training and supervision will be conducted by Drs. [name] and [name] as the RNs begin coaching caregiver participants. As part of this supervision, audio-recordings of coaching sessions will be reviewed by independent raters using the Behavior Change Technique taxonomy. Two trained raters will judge three randomly selected session recordings for each coach. Raters will assess completeness and thoroughness of the therapeutic techniques used, calculating intraclass correlation coefficients as a measure of interrater reliability. RNs who receive less than moderate ratings will receive individual session supervision. If an RN receives a low rating on any session, s/he will be required to undergo additional training and will be suspended from coaching study participants until the deficiencies are remedied. We have had success in this approach for recruiting, training, and retaining health coaches engaged in prior trials.

**C.7. Internet Access**. We will offer a variety of Internet options to participating caregivers. We will offer tablet devices, which are versatile for allowing privacy, to all participants. The tablet uses an embedded computer camera capable of full 2-way duplex video and audio transmissions for real-time communication. Existing broadband Internet connection is not required because we supply devices with mobile connectivity. Technology experts (Caryl Technologies, with whom we have worked in the past) will train research staff to set up Internet service and devices during an in-person visit and ensure that the system is functioning well before research procedures begin. Caregivers will be left with a step-by-step manual and the research office phone number in case technology issues occur. If they wish to use their own computer, we will locate the site on their computers and ensure that it functions properly. We will provide a camera for anyone in the ViCCY arm who wishes to use her/his own computer. If their personal technology proves to be inadequate, we will offer a tablet to ensure access to the website and the intervention.

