Coach Training Standardize training to ensure that it is conducted similarly for all RNs. Train RNs to well-defined performance criteria	
 
Track attrition (Research Assistants (RAs), RNs, participants) and reasons for dropout
 
Train RNs together using standardized training manuals and the same instructor
 
Design training to accommodate individual styles while assuring standardization
 
Specify performance criteria a priori
 
Provide remedial training immediately when problems are detected
 

Treatment Delivery Monitor and control for treatment differences	
 
Monitor all encounters, with deviations from protocol addressed quickly
 
Assure that a single RN is assigned to provide ViCCY for each caregiver for continuity
 
Randomly choose 3 early ViCCY sessions per RN to audio-record and rate for fidelity
 
Provide routine supervisory oversight using fidelity ratings to minimize decay or drift
 
Assure that RNs self-monitor, completing an intervention log after each contact
 

Treatment Enactment Monitor and control for participant perceptions of RN differences (e.g., warmth, credibility)	
 
Assess participant perceptions of RNs' characteristics through intermittent phone calls
 
Give feedback to RNs and mentor them to rectify complaints
 
Analyze treatment enactment data after 50%, 75%, and 100% of participants are recruited and compare by group (ViCCY and HI)
 

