## **Adequacy of Protection Against Risks**

Recruitment and Informed Consent. After approval by the Institutional Review Board (IRB) at Penn, the research staff will work with staff from the HF clinic to identify eligible caregivers for referral to us. If enrollment from the clinic is slow we will also look for hospitalized HF patients. Once identified, those caregivers will be contacted by the providers to ask about their willingness to speak with the study team. Those agreeing to speak with us will have the study carefully explained to them by the research staff. Potential participants will be fully informed regarding the interventions and the schedule of the data collection. Those willing to be screened will undergo preliminary screening to assess inclusion and exclusion criteria.

Written informed consent will be obtained from caregivers and HF patients. Those who agree to participate will be asked to read and sign the consent form with integrated HIPAA authorization information (i.e., specifics about data elements to be collected and use of the private information). The consent form will specify that some intervention sessions will be audiotaped to ensure the quality of the intervention and judge treatment fidelity. We will explain that these audiotapes will be transcribed for analysis and then destroyed. The RAs will answer questions and make sure that the procedures that are to be used are fully understood.

As stress from study participation is the most concerning risk to caregivers, we will systematically monitor to assure that we identify it. We anticipate that stress may result in early withdrawal so we will monitor withdrawal rates methodically in each group. If a participant withdraws, reasons will be carefully noted.

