Stress. To minimize the risk of stress during data collection the RAs will be trained to be supportive and helpful to participants with questions about data collection. If a participant becomes stressed during data collection because of the questions asked, the burden of data collection, or for other personal reasons, data collection will be terminated, delayed, or abbreviated to only the most essential items (e.g. primary outcome variable). Significant stress will be reported to the Project Manager who will contact the caregiver to discuss the issue if indicated (the PI is blinded). The RAs will be trained to detect any signals that the participant is becoming upset before stress escalates. In a prior study we hired nursing and psychology students as RAs, which facilitated the assessment and management of participant stress during data collection.

RAs will be required to have sufficient maturity and background to interact appropriately with ill, aging, stressed individuals. The protocol for training of RAs, detailed in our operations manual, addresses enrollment methods and the collection of data in a uniform manner. Training for RAs in data collection will occur during a two-day period prior to beginning subject enrollment. Training will begin with classroom instruction, including the purpose and background on each measure, importance of strict adherence to the standardized protocol, step-by-step instruction for survey administration, criteria for aborting testing and the procedure for audiotaping sessions and transmitting data. RAs will be trained to ensure that they do not prompt subjects with verbal or nonverbal cues. Training will include practice administering all tests. Consistency in data collection procedures will be assessed and reinforced during routine staff meetings. Retraining and retesting will be done immediately if a new RA is hired and annually thereafter. The PI and the Project Manager will meet weekly or bi-weekly with staff (in-person or by video) to discuss issues of enrollment and data collection. All decisions will be logged and filed for future reference. All issues will be reported immediately to the IRB and the Data Safety Monitoring Board, as discussed in that plan.

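### The blinding claim in C.4.d does not fit the plan's own text on notification, coach supervision and by-arm review

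*Combined protocol and SAP*

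**What the plan says.** The claim is in C.4.d (Randomization and Blinding): "Investigators and all staff involved in collecting assessment data will be" blind to arm up to database lock. Only the nurse who delivers the intervention and the caregivers are declared unblinded. C.11 repeats that research assistants (RAs) are blinded when they collect utilization data, and the Stress paragraph of Protection Against Risk says the PI is blinded.

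The text that has to fit with this claim is:

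- C.4.d, on notification: "The Project Manager will notify the study staff and participants of their group assignment (ViCCY or HI only". No exception is made for assessors or investigators.
- Protection of Human Subjects, on the same step: "Study nurses and caregiver participants will be notified of their group assignment by the Project Manager".
- C.6.a (Health coaches): "weekly training and supervision will be conducted by" two doctors, names removed, once the nurses start coaching participants.
- C.7 (Internet Access): trained research staff set up devices in person, and "We will provide a camera for anyone in the ViCCY arm who wishes to use her/his own computer".
- C.8, Table 4, Treatment Enactment: "Analyze treatment enactment data after 50%, 75%, and 100% of participants are recruited and compare by group (ViCCY and HI".
- Adequacy of Protection Against Risks, on withdrawal: "we will monitor withdrawal rates methodically in each group".
- Protection Against Risk, on RA training: it includes "criteria for aborting testing and the procedure for audiotaping sessions and transmitting data".

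**The concern.** The primary outcome, the Health Self-Care Neglect score at 6 months, is self-reported by telephone interview from caregivers who know their arm. An interviewer who also knows it can probe or record differently. An investigator who knows it can pass it on, because the PI and the Project Manager meet staff weekly or bi-weekly. Blinding of assessors and investigators is one of the protections the plan relies on, and a report of the trial would be expected to state it. If the procedures disclose the arm to people whom C.4.d calls blinded, the report would claim a property that the trial did not have.

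**Working it through.** The plan states no figure on this point to reproduce. The check sets the passages side by side, then places the by-arm reviews on the calendar.

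**1. Who is told.** C.4.d says study staff and participants. Human Subjects says study nurses and participants. Read literally, the first group includes RAs and the second does not. The Project Manager, who passes on the assignments, must know them, yet is missing from the unblinded list in C.4.d.

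**2. Who learns the arm by supervising.** Only ViCCY caregivers have coaching sessions, so a supervisor who discusses a caregiver's session knows that caregiver's arm. Names are removed in C.6.a, so it is an inference that the supervisors are investigators. The inference is strong, because C.1 lists health coaching and motivational interviewing as PI expertise and intervention work with caregivers as a co-investigator's. If either supervisor is an investigator, the C.4.d claim fails for that person. If neither is, C.4.d still omits them from its unblinded list.

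**3. What could reveal the arm to an RA.** Under C.4.b, tablet training comes after randomization. C.7 assigns set-up to research staff without further definition, and the camera for a caregiver's own computer goes to ViCCY only. RA training covers audiotaping, and the audiotaping described in Protection of Human Subjects is of ViCCY sessions. Table 4 has an unnamed person telephone participants about their perceptions of the nurses. No sentence assigns these tasks to the RAs who make outcome calls, and none keeps them apart.

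**4. When by-arm review happens.** C.14 places its group comparisons after lock, but the enactment reviews are tied to recruitment.

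Inputs: N = 250 (C.13); accrual r = 10 a month, from 63 × 0.15 = 9.45 rounded up; 30 months allowed for enrolment (C.4.a), so r = 250/30 = 8.33 at the slowest; outcome at 6 months. Assumptions: even accrual and no dropout.

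- Time of review at fraction f: t = 250f / r.
- Six-month assessments outstanding: 250 − r(t − 6) = 250(1 − f) + 6r.
- Last six-month assessment: 250/r + 6.

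| r per month | Reviews at months | Outstanding at 50%, 75%, 100% | Last 6-month call |
|---|---|---|---|
| 10 | 12.5, 18.75, 25 | 125 + 60 = 185; 62.5 + 60 = 122.5; 0 + 60 = 60 | 31 |
| 9.45 | 13.2, 19.8, 26.5 | 181.7; 119.2; 56.7 | 32.5 |
| 8.33 | 15, 22.5, 30 | 175; 112.5; 50 | 36 |

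The last 12-month call is 6 months later again (month 37 at 10 a month, month 42 at the slowest rate). All three reviews therefore precede lock. Neither Table 4 nor the withdrawal text says who receives the results.

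**The case against.** The other side has several fair points.

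- **Study staff may mean the nurses.** Human Subjects says so, C.11 says RAs are blinded, and participant distress is routed to the Project Manager precisely because the PI is blinded. This stands as far as it goes: a reader might infer that outcome RAs are told each caregiver's arm, and the documents do not show that. What remains is a conflict of wording on the central question of who is told.
- **Supervision need not expose every case.** C.6.a does not say that supervisors discuss every caregiver, and the recordings, three per coach, go to independent raters. A reader might infer that the supervisors know the arm of the whole ViCCY group. That is only an upper bound. The arm is known for the cases discussed, which is enough to defeat an unqualified claim.
- **There are other safeguards.** RAs are trained in a standardized protocol and not to prompt, answers go straight into REDCap, and treatment expectancy is measured in both arms. This stands: interviewer blinding is not the sole protection.
- **By-arm tables are aggregate and contain no outcome scores.** They do not identify an individual's arm. A reader might also infer that they could steer the modelling choices left open in C.14, but enactment and withdrawal data say nothing about how neglect scores should be transformed or modelled.
- **The RA points are indirect.** Both arms are offered tablets, and the audiotaping phrase could refer to data-collection sessions, since the data storage text mentions audiotaped interviews. This is fair, so the point is a missing separation of tasks, not a shown breach.
- **Details may sit elsewhere.** The text refers to a DSMB plan and an operations manual, neither of which is among the documents. They may name recipients, but C.4.d would still need correcting.

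**Conclusion.** The concern holds as an inconsistency in the stated blinding and should be corrected. As written, C.4.d cannot be true for a coaching supervisor who is an investigator. It disagrees with Human Subjects on who is notified, and it omits the Project Manager from the unblinded list. Assessor blinding is asserted, but no procedure protects it. By-arm review takes place while between 50 and 185 of the 250 primary assessments are still due, depending on the review and the accrual rate, and its recipients are not named.

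The documents support no estimate of the resulting bias in the primary outcome, and no sample size, power or alpha figure changes. Confidence is medium: the supervision point rests on inferring that at least one supervisor is an investigator, and the RA point rests on the absence of a safeguard.

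**What to change.** 1. Change the notification sentence in C.4.d to match Human Subjects, so that only coaches and participants are told the assignment.
2. List the coaching supervisors and the Project Manager as unblinded. Narrow the investigator-blinding claim, and the statement under Protection Against Risk that the PI is blinded, to fit. Keep the supervisors out of RA supervision and out of analysis decisions before lock.
3. State that RAs who make outcome calls do no device set-up after allocation, no recording of coaching sessions and no calls about perceptions of the nurses. The Project Manager or other non-assessing staff should make the perception calls. The coaches should not, since they would be collecting ratings of themselves and weakening the fidelity check.
4. Send by-arm enactment and withdrawal tables only to the Project Manager and the DSMB until lock.

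The cost is a narrower blinding claim and some tasks moved among existing staff. Sample size, visits and measures are unaffected.
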